### Research question

How does variation in assessment and management of dysphagia in acute stroke affect development of stroke-associated pneumonia?

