## **Primary Outcome**

The primary outcome is association with stroke-associated pneumonia

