## **Overview of Study design**

A mixed mode survey design comprising of a self-administered electronic survey with a secondary option of a postal survey. The sample frame was

Routinely Admitting, and Non-Routinely Admitting Acute Stroke Hospital Teams registered on the Sentinel Stroke National Audit Programme (SSNAP) register. The survey population was Speech and Language Therapy (SLT) Clinical Leads for Acute Stroke in Hyper/Acute Hospital Stroke Units in England and Wales. The total survey population were surveyed. Survey participants were asked to respond about practice on behalf of the Stroke Unit rather than as an individual practitioner.

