## **Statistical analyses**

Only completed surveys will be analysed. The survey data will be analysed using descriptive and inferential statistics. Descriptive statistics will include analysis of categorical and continuous data. Descriptive statistics of categorical variables will be frequency analysis i.e., percentage of the different categories within each variable. For example, proportion of Hospital Teams that are Routinely Admitting Teams and Non-Routinely Admitting Acute Teams. Categorical data will be visualised with bar and pie charts. The evaluation method for continuous data (incidence of pneumonia) will be mean and standard deviation to evaluate the dispersion of pneumonia incidence across the hospital teams and visualised using histograms.

Inferential statistics (linear regression analysis) will be used to test the hypotheses and explore if there is an association between the dependent variable (incidence of stroke-associated pneumonia) and independent binary variables: 1. Hospital Teams that use Water only dysphagia screening protocols (DSP) versus Hospital Teams that use water and other consistencies DSPs, 2. Hospital teams that use written guidelines for the first specialist clinical bedside swallow assessment versus Hospital teams that do not use written guidelines for the first specialist swallow assessment, 3. Hospital Teams that insert Nasogastric Tubes (NGTs) overnight have increased risk of SAP compared to Hospital Teams that do not insert NGTs overnight and 4. Hospital Teams with a written oral care protocol versus those do not have a written oral care protocol. Linear regression analysis will be visualised using Model Summary tables with Coefficients and 95% Confidence Intervals.

The proposed analysis for each variable is given in Table 1.

Table 1 – Proposed analysis for each variable

Variable	Data Source (s)	Values	Type of variable	Analysis approach	Methods for summarising data
Hospital Team	Survey Question #3 Please type the name of your hospital and select from the drop-down menu. SSNAP 2019 Team Centred 72-hour cohort data	1 = Routinely Admitting Team 2 = Non-Routinely Admitting Team	Categorical – Nominal - dichotomous	Descriptive statistics (frequencies) - Proportion of completed surveys for Routinely Admitting Team and Non-Routinely Admitting Acute Teams by SCN Region	Table

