	Survey Question #9 Does the dysphagia screening protocol only use water (Level 0 Thin Fluids) i.e., 100% water? SSNAP 2019 Patient Centred Post 72hr cohort data prescription of antibiotics for a newly diagnosed pneumonia	1= Yes 2= No  SPSS Recoded (dummy variables) 0=Yes 1=No	Categorical – Nominal - dichotomous  Dependent variable – outcome - incidence of SAP Independent variable – predictor – Water only DSPs versus water and other consistencies DSPs	Descriptive statistics (frequencies) - Proportion answering yes or no AND Inferential statistics (Linear Regression) Null hypothesis – There is no difference in incidence of pneumonia using a dysphagia screen that uses 100% water compared to water and other consistencies	Bar chart  Model Summary Table with coefficients and 95% Confidence Intervals
	Survey Question #10 What is the maximum amount of water given? Please indicate the maximum amount in millilitres (mls).	1=5, 2=10, 3=15, 4=20, 5=25, 6=50, 7=100, 8=150, 9=200	Categorical Ordinal	Descriptive statistics (frequencies)- proportion by selected choice	Bar chart

	Survey Question #11 Which International Dysphagia Diet Standardisation Initiative (IDDSI) levels are included in the dysphagia screening protocol?	1= Level 0 Thin, 2= Level 1 Slightly Thick, 3=Level 2 Mildly Thick, 4=Level 3 Moderately Thick, 5=Level 4 Puree, 6=Level 5 Minced and Moist, 7=Level 6 Soft & Bite Size, 8=Level 7 Regular Easy to Chew, 9=Level 7 Regular	Categorical – Ordinal	Descriptive statistics (frequencies) - Proportion by selected choice	Bar chart
	Survey Question #12 Which IDDSI level consistency do you screen with first?	1= Level 0 Thin, 2= Level 1 Slightly Thick, 3=Level 2 Mildly Thick, 4=Level 3 Moderately Thick, 5=Level 4 Puree, 6=Level 5 Minced and Moist, 7=Level 6 Soft & Bite Size, 8=Level 7 Regular Easy to Chew, 9=Level 7 Regular	Categorical – Ordinal	Descriptive statistics (frequencies) - Proportion by selected choice	Bar chart
Delays in dysphagia screening	Survey Question #14 Below is a list of reasons for delays in stroke patients being screened for dysphagia. How applicable are each of these reasons for delays in stroke patients being screened for dysphagia in your stroke unit?	1=Strongly applicable 2=Somewhat applicable 3=Somewhat less applicable 4=Strongly not applicable	Categorical – Nominal	Descriptive statistics - Likert Scale	Bar chart/Free text

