	SSNAP 2019 Patient Centred Post 72hr cohort data prescription of antibiotics for a newly diagnosed pneumonia	SPSS Recoded (dummy) variables 0=Yes 1=No	outcome - incidence of SAP Independent variable – predictor – Written guidelines (versus clinical reasoning and hypothesis generation)	Null hypothesis – Using written guidelines for the first specialist swallow assessment will not be associated with incidence of pneumonia	coefficients and 95% Confidence Intervals
Components of the specialist swallow assessment	Survey Question #21 In your Stroke Unit, what does the first clinical (bedside) swallow assessment typically involve?	1= PMH, 2= HPC, 3= Assessment of cognitive-communication status, 4= Assessment of respiratory status, 5= Cranial Nerve examination, 6=Cough reflex testing, 7= Assessment with oral intake 8= Assessment with postural strategies, 9= Assessment with swallowing manoeuvres, 10= Other	Categorical – Nominal	Descriptive statistics (frequencies) – Proportion by selected choice	Bar chart/Free text
	Survey Question #22 What International Dysphagia Diet Standardisation Initiative (IDDSI) levels are typically included in the first clinical (bedside) swallow assessment?	1=Level 0 Thin, 2= Level 1 Slightly Thick, 3= Level 2 Mildly Thick, 4=Level 3 Moderately Thick, 5= Level 4 Puree, 6=Level 5 Minced and Moist, 7=Level 6 Soft & Bite Sized, 8= Level 7 Easy to Chew, 9=Level 7 Regular	Categorical – Ordinal	Descriptive statistics (frequencies) - Proportion by selected choice	Bar chart
	Survey Question #23 Please describe what postural techniques are assessed? Examples include chin-down posture, chin-up posture, head	Free text		Free text	

	rotation (turn to side) and head tilt. These examples are not exhaustive.				
	Survey Question #24 Please describe what swallowing manoeuvres are assessed? Examples of include effortful swallow, Mendelsohn manoeuvre, supraglottic swallow and super-supraglottic swallow. These examples are not exhaustive.	Free text		Free text	
Delays in specialist assessment	Survey Question #25 Below is a list of reasons for delays in stroke patients receiving a clinical (bedside) swallowing assessment. How applicable are each of these reasons for delays in stroke patients receiving a clinical swallowing assessment in your stroke unit?	1=Strongly applicable 2=Somewhat applicable 3=Somewhat less applicable 4=Strongly not applicable	Categorical – Nominal	Descriptive statistics - Likert Scale	Bar chart/Free text

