Time from decision to non-orally feed and feeding by NGT	Survey Question #32 In patients who are unable to maintain adequate nutrition and fluids orally, please indicate typically the number of hours from when the decision is taken to non-orally feed and the beginning of feeding by an NGT?	1=< 6 hours 2>= 6 - < 12 hours 3>= 12 - < 24 hours 4>= 24 - < 48 hours	Categorical - Nominal	Descriptive statistics (frequencies) - Proportion by selected choice	Bar chart
Confirmation of position of NGT	Survey Question #33 How does your stroke unit check the position of the NGT before starting feeding?	1= pH testing of NGT aspirate, 2= Chest radiography if no aspirate obtained or pH above recommended level, 3= Routinely perform chest radiography, 4= Other	Categorical - Nominal	Descriptive statistics (frequencies) - Proportion by selected choice	Pie Chart/Free text
Management strategies	Survey Question #34 In cases of inadvertent NGT removal, does your stroke unit typically use any of the following management strategies?	1= Mittens, 2= Nasal retention device, 3= 1:1 staff: patient supervision, 4=Other	Categorical - Nominal	Descriptive statistics (frequencies) - Proportion by selected choice	Pie Chart/Free text

Maximum number of NGTs	Survey Question #36 In case of inadvertent NGT removal, what is the maximum number of times reinsertion of the NGT is attempted in any patient?	1=Once, 2= Twice, 3= Three times, 4= If more than three, please state how many	Categorical – Ordinal	Descriptive statistics (frequencies) - Proportion by selected choice	Pie Chart/Free text
Overnight NGT insertion	Survey Question #37 Are NGTs inserted overnight? SSNAP 2019 Patient Centred Post 72hr cohort data prescription of antibiotics for a newly diagnosed pneumonia	1=Yes 2=No  SPSS Recoded (dummy) variables  0=Yes 1=No	Categorical – Nominal – dichotomous  Dependent variable – outcome - incidence of SAP Independent variable – predictor – Insertion of NGT overnight	Descriptive statistics (frequencies) - Proportion answering yes or no AND Inferential statistics (Linear Regression) Hypothesis – Hospital Teams that insert NGTs overnight have increased risk of SAP compared to Hospital Teams that do not insert NGTs overnight.	Bar chart  Model Summary Table with coefficients and 95% Confidence Intervals

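### Team type (routinely or non-routinely admitting) is recorded for every team but enters none of the regressions for Hypotheses 1 to 4

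*SAP*

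**What the plan says.** - **Sample.** Under Overview of Study design, the sample frame is "Routinely Admitting, and Non-Routinely Admitting Acute Stroke Hospital Teams registered on the Sentinel Stroke National Audit Programme (SSNAP) register". The Sampling plan leaves 166 teams after exclusions.
- **Team type.** Table 1 (Hospital Team, Survey Question #3) codes it 1 or 2. The only analysis given is descriptive: "Proportion of completed surveys for Routinely Admitting Team and Non-Routinely Admitting Acute Teams by SCN Region". The text under Statistical analyses likewise mentions it only as an example of a proportion.
- **Models.** Under Statistical analyses, linear regression is to "explore if there is an association between the dependent variable (incidence of stroke-associated pneumonia) and independent binary variables", followed by the four practices. The inferential rows of Table 1 match this. The row for Hypothesis 1 reads "Independent variable – predictor – Water only DSPs versus water and other consistencies DSPs" and the row for Hypothesis 3 "Independent variable – predictor – Insertion of NGT overnight". The rows for Hypotheses 2 and 4 name written assessment guidelines and a written oral care protocol. No covariate, stratum or interaction is named in the text or in Table 1.
- **Outcome.** An annual 2019 pneumonia percentage per team, with no adjustment described.
- **Aim.** Primary Outcome: "The primary outcome is association with stroke-associated pneumonia". Research question: "How does variation in assessment and management of dysphagia in acute stroke affect development of stroke-associated pneumonia". Hypotheses 3 and 4 speak of increased and reduced risk.
- **Sensitivity analysis.** The examples are low response from a region and data from the Covid-19 period. Team type is not mentioned.

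**The concern.** This is an observational comparison between teams, and the SAP itself separates those teams by how they admit patients. If that distinction goes with both the use of a practice (overnight tube insertion, say) and the team's pneumonia percentage, an unadjusted coefficient attributes to the practice something that belongs to the type of team. The error could create an association, hide one or reverse it.

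An unadjusted coefficient does estimate an association between teams, which is all the Primary Outcome section claims. The research question and Hypotheses 3 and 4 go further, to effect and risk. None of the specified outputs crosses team type with a practice or with pneumonia incidence, so a reader could not judge how far a coefficient reflects the practice and how far the team type.

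**Working it through.** **What the document settles.** Team type appears in the sample frame, in the descriptive text and in the first row of Table 1. It is absent from the regression sentence and from all four inferential rows. The SAP does not say whether the four practices are fitted separately or jointly. A joint model would adjust each practice for the other three, but still not for team type.

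**What it does not settle.** It gives no pneumonia incidence by team type, no split of the 166 teams by type and no between-team standard deviation. On practice by team type, Missing data methodology points both ways. A lead responsible for two teams is asked for two surveys, so answers may differ. If only one survey arrives and the lead confirms the same answers apply, they are copied to the second team. The SAP has no figure to reproduce, so what follows is illustration only: every input except the 166 teams is assumed.

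**Inputs.** *r* = share of teams routinely admitting; *p1*, *p0* = practice prevalence in routinely and non-routinely admitting teams; *d* = gap in pneumonia incidence between team types, in percentage points; *c* = share of non-routinely admitting teams with copied answers, which replaces *p0* by *c·p1* + (1 − *c*)·*p0*. The true practice effect is set to zero.

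**Bias with one practice per model:** *d* × [P(routinely admitting | practice) − P(routinely admitting | no practice)]. At *r* = 0.8:

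- Modest (70%/40%, *d* = 2): prevalence 0.56 + 0.08 = 0.64; bracket 0.56/0.64 − 0.24/0.36 = 0.875 − 0.667 = 0.208; bias 0.42 points.
- Strong (80%/30%, *d* = 3): prevalence 0.64 + 0.06 = 0.70; bracket 0.64/0.70 − 0.16/0.30 = 0.914 − 0.533 = 0.381; bias 1.14 points.
- Strong, *c* = 0.5: *p0* becomes 0.55; bracket 0.64/0.75 − 0.16/0.25 = 0.853 − 0.640 = 0.213; bias 0.64 points.
- Equal prevalence, *d* = 0 or *c* = 1: bias 0.
- Extreme corner (*r* = 0.7, 80%/30%, *d* = 5): 5 × 0.462 = 2.3 points, in either direction.

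**Bias with all four practices in one model,** assumed independent within team type and sharing the same prevalences. With *P* the overall prevalence and δ = *p1* − *p0*, the bracket becomes *r*(1 − *r*)δ / [*P*(1 − *P*) + 3*r*(1 − *r*)δ²]. Strong setting: 0.08 / (0.21 + 0.12) = 0.242, so the bias is 0.73 points.

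**False rejection at two-sided 5%,** unadjusted model, *r* = 0.8, normal errors (6,000 simulated data sets per setting; 3,000 for the joint model):

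| Setting | 100 teams, SD 6 | 166 teams, SD 4 |
|---|---|---|
| No link to practice (50%/50%, *d* = 3) | 5.1% | 5.4% |
| No link to pneumonia (80%/30%, *d* = 0) | 4.9% | 5.3% |
| Modest | 5.8% | 9.2–9.7% |
| Strong | 13.6% | 36.4% |
| Strong, half copied | 6.7–7.2% | 13.4–13.7% |
| Strong, all copied | 4.4–5.1% | 4.7–5.0% |
| Strong, joint model | 8.0% | 16.9% |

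A separate normal approximation with equal predictor groups, SE = SD·√(4/N), gives similar sizes. For a bias of 0.4 points, rejection runs from 6.9% (100 teams, SD 5) to 13.8% (166 teams, SD 3).

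**The case against.** The strongest reply is that the SAP contradicts nothing here. It promises an association, and an unadjusted regression delivers one. Neither link needed for bias is evidenced, a possible confounder can be named for almost any unadjusted model, and the larger figures need inputs with no source. If 95% of teams were routinely admitting, the same formula gives only 2 × 0.066 = 0.13 points in the modest setting and 3 × 0.136 = 0.41 in the strong one. Copied answers would weaken the link further. Team type is chosen partly for convenience, and adjusting for it leaves other case-mix differences. The sensitivity section's list is only by way of example, so a team-type analysis is not ruled out.

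Most of this is fair and limits the claim: bias is not shown, and the illustrations are not information about this study. What it does not answer is the mismatch between an aim worded as effect and risk and models with no control for a distinction the SAP itself draws. An analysis that is merely not excluded is not a planned one. The SAP describes survey collection as already completed, so a later choice to adjust could be influenced by the results.

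**Conclusion.** The point holds. Team type is recorded, used only descriptively, and in none of the models for Hypotheses 1 to 4; that much is certain from the text. The consequence is uncertain: zero if either link is absent or if all non-routinely admitting teams carry copied answers, small in the modest setting, and material only with strong imbalance and a clear incidence gap. The case for change rests on the specification and the low cost of correcting it, not on the illustrative figures. It should be fixed before the models are run; confidence is medium because the size cannot be found from the SAP.

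**What to change.** Under Statistical analyses, and in the four inferential rows of Table 1, add: *Team type (routinely / non-routinely admitting) will be included as a covariate in the model for each hypothesis. The adjusted coefficient and 95% CI will be reported beside the unadjusted one.* Under Sensitivity analysis, add a run restricted to routinely admitting teams.

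Team type is the practical choice: already held, binary, one degree of freedom. Key indicators 4.5 and 4.6 (Data sets) are less suitable because they measure timing of the swallow screen and assessment and may lie on the path from practice to pneumonia. Region would use more degrees of freedom; the number of regions is not given.

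The cost is SAP wording and a few extra model runs. In one-practice models the standard error grows by 1/√(1 − φ²), where φ is the correlation between practice and team type. Over the assumed settings the factor is 1.00 to 1.14, and at most 1.04 with half the answers copied. If team type is unrelated to pneumonia, that precision is all that is lost. At an assumed 70% to 90% share, the restricted run keeps about 116 to 149 of 166 teams, or 70 to 90 of 100. Residual case-mix confounding remains and should be stated as a limitation.

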**How does dysphagia assessment in acute stroke affect pneumonia?**

**Statistical Analysis Plan**

## Statistical Analysis Plan

### Research background

Stroke-associated pneumonia (SAP) is a common post stroke infection affecting 14% of patients (Kishore et al. 2015) and is associated with an increased risk of hospital mortality (Westendorp et al. 2011) and prolonged hospital stay (Finlayson et al. 2011). The combination of stroke-induced immune-deficiency and aspiration of oropharyngeal secretions and gastric contents into the lungs secondary to impaired consciousness and dysphagia predisposes patients to SAP in the first few days post stroke (Hannawi et al. 2013). Patients with dysphagia with confirmed aspiration have an 11-fold increased risk to SAP (Martino et al. 2005). However, up to half of patients with SAP do not aspirate (Westendorp et al.), which reflects SAP's multifactorial pathophysiology.

There is wide variation in the assessment and management of dysphagia in acute phase stroke and there is the potential for a range of medical interventions and clinical processes to be associated with risk of SAP (Eltringham et al. 2018, 2019). This research aims to find out how methods of dysphagia assessment and clinical management during the first 72 hours of admission to hospital affect the risk of stroke patients developing SAP and what care processes and interventions specific to patients with dysphagia affect the risk of stroke patients developing SAP during acute phase stroke.

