## Method for analysing the data for incidence of stroke-associated pneumonia

Stroke-associated pneumonia (SAP) will be defined as the administration of antibiotics for a new clinical diagnosis of pneumonia in the first 7 days after admission as determined by the treating physician. SSNAP Patient Centred Post 72-hour quarterly data for Antibiotics for newly acquired pneumonia in the first 7 days from clock start will be used to calculate an annual 2019 pneumonia percentage for each team to measure the dispersion of the of pneumonia incidence across the teams.

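### Hypotheses 1 to 4 are tested on crude team pneumonia percentages with no case-mix adjustment, so a difference between the teams' patients may be read as an effect of practice

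*SAP*

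**What the plan says.** The SAP, Statistical analyses, states: "Inferential statistics (linear regression analysis) will be used to test the hypotheses". The regression is also to "explore if there is an association between the dependent variable (incidence of stroke-associated pneumonia) and independent binary variables". It then lists four binary practice variables: water-only screening, written guidelines for the first specialist assessment, overnight nasogastric tube (NGT) insertion and a written oral care protocol. Table 1 gives each hypothesis one predictor and no covariate. The entry for Hypothesis 1, for example, reads "Independent variable – predictor – Water only DSPs versus water and other consistencies DSPs".

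The method section for the outcome says that quarterly registry data "will be used to calculate an annual 2019 pneumonia percentage for each team". No standardised or risk-adjusted rate is mentioned, and the percentage is handled as a continuous variable across teams.

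The Data sets section adds two registry items, key indicators 4.5 and 4.6. Both measure timeliness of care, not patient characteristics, and neither is given a place in a model. Team type (routinely admitting or not) is used only descriptively. The two examples under Sensitivity analysis are regional response and the Covid-19 period.

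The Research question is: "How does variation in assessment and management of dysphagia in acute stroke affect development of stroke-associated pneumonia". Hypotheses 3 and 4 are worded as increased and reduced risk. The Research background says: "Patients with dysphagia with confirmed aspiration have an 11-fold increased risk to SAP".

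**The concern.** The unit of analysis is the hospital team, and practices were not allocated to teams at random. A team's crude pneumonia percentage reflects both what it does and whom it treats. The SAP names strong patient-level determinants of the outcome and then leaves them out of every model.

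If the teams with and without a practice differ in stroke severity, consciousness level or dysphagia burden, the coefficient carries that difference. It could then have the wrong size or the wrong sign. Hypothesis 3 is the most exposed. If teams that insert NGTs overnight tend to have sicker patients, the bias runs in the hypothesised direction and would look like confirmation. That link is plausible, but it is an assumption; the SAP does not document it.

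This is not a detail left to a protocol. The SAP fixes the dependent variable, predictor, coding and data source for each hypothesis, and so fixes an unadjusted analysis. Surveying more teams would not remove the bias; it would only narrow the interval around a biased value.

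**Working it through.** The SAP gives no power calculation, significance level, effect size or between-team SD, so it has no figure to reproduce. What follows shows how large the problem could be.

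**Inputs from the SAP**
- 166 teams, the ceiling (Sampling plan).
- 14% overall incidence, an 11-fold risk with confirmed aspiration, and up to half of pneumonia patients not aspirating (Research background).

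**Assumptions (not in the SAP)**
- Two-sided 5% test; teams split 50:50 on the practice; no true effect of practice.
- Case mix explains a share R² of between-team variance, 25% to 50%.
- The practice groups differ in mean case mix by d standard deviations (d = 0, 0.25, 0.5).
- Where percentage points are shown, a between-team SD of 4 points.

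**Step 1: chance of rejecting a true null**

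Bias in the coefficient = √R² × SD × d. Standard error = 2 × SD / √N. So bias/SE = √R² × d × √(N/4), and the SD cancels. The rejection probability is Φ(bias/SE − 1.96) + Φ(−bias/SE − 1.96).

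For N = 166, √(166/4) = 6.442. For N = 83 (half the teams responding), √(83/4) = 4.555.

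| d | R² | bias/SE, N = 166 | Rejection, N = 166 | bias/SE, N = 83 | Rejection, N = 83 |
|---|---|---|---|---|---|
| 0 | any | 0 | 5% | 0 | 5% |
| 0.25 | 25% | 0.805 | 13% | 0.569 | 9% |
| 0.25 | 50% | 1.139 | 21% | 0.805 | 13% |
| 0.5 | 25% | 1.611 | 36% | 1.139 | 21% |
| 0.5 | 50% | 2.278 | 62% | 1.611 | 36% |

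**Step 2: the same bias in percentage points**

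With SD = 4, the 95% half-width at N = 166 is 1.96 × 2 × 4 / √166 = 1.22 points. The bias is:
- d = 0.25: 0.5 × 4 × 0.25 = 0.50 to 0.707 × 4 × 0.25 = 0.71 points.
- d = 0.5: 1.00 to 1.41 points.

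**Step 3: what the SAP's own risk figures imply per point of imbalance**

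Let q be the share of patients who aspirate. Read the 11-fold figure as a risk ratio against all other patients, which is an assumption because the SAP gives no comparator. Risk in non-aspirators is p₀ = 14% / (1 + 10q). Each extra percentage point of aspirating patients then raises the expected pneumonia percentage by 10 × p₀ × 0.01.

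If at most half of cases are in non-aspirators, 1 − q ≤ 11q, so q is at least 1/12 (8.3%). Values of 20% and 30% are assumed.
- q = 8.3%: p₀ = 7.64%, shift 0.76 points.
- q = 20%: p₀ = 4.67%, shift 0.47 points.
- q = 30%: p₀ = 3.50%, shift 0.35 points.

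A 2-point imbalance in aspirating patients would therefore shift the crude percentage by 0.70 to 1.53 points with no effect of practice, about the range in Step 2. Whether such an imbalance exists cannot be known from the SAP.

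**The case against.** The best defence is that the SAP claims only association: that is the word in the Primary Outcome and in the regression description. A crude association is a legitimate descriptive quantity, and confounding arises only if case mix differs between the practice groups. The SAP does not show that it does. Nothing in it links overnight tube insertion or formal protocols to sicker patients; its rationale for Hypothesis 3 concerns junior staff and confirmation of tube placement. For Hypothesis 1 there is no stated reason why the choice of screening consistency should follow severity. The background also calls the condition multifactorial and notes that many cases occur without aspiration.

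Much of this stands. A reader might infer that a case-mix difference is certain to be reported as an effect of practice, or that every coefficient is biased. The SAP supports neither. Nor does it support a single headline error rate: d is unknown, and at d = 0 the test keeps its 5% level.

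The defence does not dispose of the point. The research question asks how practice affects pneumonia, and Hypotheses 3 and 4 speak of risk, so an association will invite that reading. The plan has no means of detecting an imbalance if there is one. The SAP does not say whether the four indicators enter one model or four; entering them jointly would adjust practices for each other, not for patients.

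**Conclusion.** The concern holds in a conditional form. All four hypotheses are tested on crude team percentages, with case mix absent from the models, the data list and the sensitivity examples. If the practice groups differ in patient severity or dysphagia burden, that difference may be read as an effect of practice.

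At d = 0.25 the false-rejection rate is more than double the nominal 5% at N = 166. At d = 0.5 it is at least seven times nominal. With half the teams, the inflation is smaller. These figures rest on the assumed R², d and even split; they illustrate sensitivity and do not estimate the actual bias. The absence of any case-mix term is established from the text and depends on none of these assumptions.

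**What to change.** 1. **Data sets:** add 2019 team-level age and stroke severity or consciousness level, for the same Patient Centred cohort as the outcome. That the registry can supply these by team is an assumption to confirm.
2. **Statistical analyses and Table 1:** make the case-mix-adjusted regression the main analysis for Hypotheses 1 to 4, name the covariates, and show the crude estimate beside each adjusted one.
3. **If the data cannot be obtained:** reword the Research question and Hypotheses 3 and 4 as crude team-level association. For each coefficient, report the imbalance that would explain it away, d = coefficient / (√R² × SD), over a stated range of R².
4. **Indicator 4.6:** do not use the number of applicable patients as a main proxy for dysphagia burden. The SAP does not define applicable or promise denominators, and the indicator is Team Centred while the outcome is Patient Centred. If denominators exist for the outcome cohort, it could serve as a labelled sensitivity analysis.

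The cost is one more registry extract, one to three model terms and some rewording. Team averages remove only part of the confounding, so the limitation should still be stated.
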